2.1.7. Hyperglycemia

Alteration in glucose refers to a permanently abnormal change in these levels. According to the ADA criteria in 2024, these alterations can be expressed through various tests, such as fasting plasma glucose with a result >100 mg/dL or glycated hemoglobin (HbA1c) with results exceeding $>5.7\%$ (39 mmol/mol) (39).

2.1.7.1. Epidemiology of Hyperglycemia

The epidemiology of blood glucose alterations is crucial for understanding the population's health status. In 2022, Baltazar in 2022 and Basto in 2023 reported the prevalence range of glucose abnormalities among higher-level students in Mexico, which ranged from 14.3% to 29% (40,41).

Similarly, in 2022, Zenteno and colleagues conducted a study in a private school in Tuxtla Gutiérrez, Chiapas, which aimed to determine the prevalence of different metabolic disorders among students at that institution. The study revealed that 25.3% exhibited hyperglycemic alterations, and 56% of them reported a sedentary lifestyle, extrapolating the risk factors for cardiovascular diseases (32).

2.1.7.2. Aetiology of Hyperglycemia

Blood glucose alterations have different degrees. The first degree refers to genetic modifications, which may involve changes in the TCF7L2 gene (which plays a role in insulin control), the CAPN10 gene (calpain 10) which is linked to glucose homeostasis, and the KCNJ11 gene (a potassium channel, Subfamily J11). The latter gene encodes a potassium channel subunit associated with insulin secretion. Additionally, (42). The environmental degree refers to diets with high consumption of saturated fats, excessive intake of sugary products, and other components, such as a sedentary lifestyle and physical inactivity (43).

2.1.7.3. Pathophysiology of Hyperglycemia

The hormone responsible for regulating blood glucose is insulin, which is produced in the pancreas, an organ that consists of two types of tissue: exocrine and endocrine. The endocrine tissue includes Langerhans islets (these islets are composed of Alpha, Beta, and Delta cells). Beta cells play a crucial role in this process, as they can produce up to 60% of active insulin and Amylin (44). Whereby, If there is any disruption in the production of active insulin by pancreatic cells, it directly leads to permanently elevated blood glucose levels. This, in turn, can result in potential health complications for the individual. *Figure 4.*

[figure not shown]

Figure 3. Behaviour of glucose in the human body. Based on González in 2020
 Source: Based in León in 2023(38).

2.2. Diagnosis and evaluation of metabolic disorders

2.2.1. Tests and Diagnosis for Determining Abdominal Obesity

There are two widely established methods for measuring abdominal fat parameters. One of them is bioimpedance (a scale that quantifies body composition using electrodes), and the second method is abdominal circumference measurement using a measuring tape, with results given in centimetres. In order to perform the abdominal circumference test, the patient should be in the anatomical position. Subsequently, the mid-axillary line is located, at the midpoint between the costal margin and the iliac crest, which has to be marked with a pen, to serve as a guide to place a certified measuring tape, to measure the circumference at the end of a normal expiration. Making at least two measurements and calculating their average (45) is recommended. The results are compared with the WHO cut-off points: >90 cm in men and >85 cm in women (46).

2.2.2. Testing and diagnosis of factors (TG and HDL) involved in dyslipidemia.

For an initial detection of dyslipidemia, it is essential to consider the following: A comprehensive medical history, including family history of cardiovascular diseases, pancreatitis, obesity, arterial hypertension, dyslipidemias, smoking, alcoholism, as well as an evaluation of diet and physical activity (47).

Additionally, laboratory testing is a better option. The lipid profile is a laboratory analysis that aims to determine the concentrations of various fats in the blood, including total cholesterol, LDL, HDL, and triglycerides. These analyses are crucial for assessing the risk of vascular and cardiovascular diseases (48). It is essential that the patient undergoes this analysis after fasting (8 to 12 hours before the test) and abstains from alcohol consumption for 24 hours. The test involves a venous puncture to collect a blood sample, which will be analyzed by authorized equipment (48). The obtained results should be correlated with established cutoff points. *Table 1*. There is a close relationship between dyslipidemia and increased hypertension, as cholesterol, LDL, and triglycerides can cause damage and blockages in arterial walls (47).

2.2.3. Test and diagnosis of systemic arterial hypertension

For the diagnosis of systemic arterial hypertension (SAH), the test must be performed with a stethoscope and a sphygmomanometer (Baumanometer) with a properly calibrated band. The process begins with the patient sitting for 5 to 10 minutes to stabilize blood pressure. Afterwards, the Baumanometer band will be wrapped around the arm, it should be 2 or 3 cm above the fold of the elbow joint. Next, the brachial artery must be palpated to be able to place the bell of the stethoscope at the level of the brachial artery (The centre of the camera must align with the brachial artery). Once these steps have been completed, the handle of the manometer will be inflated until a pressure of 160 mmHg is reached. After reaching this reference, the valve will be opened gradually with a speed of 2 to 3 mmHg/second, listening in turn to the pulsations emitted by the body to determine systolic and diastolic blood pressure

(35). If the patient obtains a systolic blood pressure of >130 mmHg and diastolic blood pressure of >80 mmHg, an alteration in blood pressure must be confirmed (36). Annex 5.

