2.1.5.6 High-density lipoproteins (HDL)

HDL has various functions, one of the most well-known being its role as a “scavenger” for cholesterol, removing excess cholesterol from arterial walls and returning it to the liver, where it is “discarded”, added to the bile and eliminated through feces, since the human body cannot degrade cholesterol on its own (28). According to the Adult Treatment Panel III (ATP III) guidelines for dyslipidemia, the cutoff points for potential risk are <40 mg/dL in men and <50 mg/dL in women (31).

2.1.5.7. Altered HDL epidemiology.

The epidemiology of HDL in individuals can be crucial for their overall health. Therefore, it constitutes a crucial field in cardiovascular health research among university students in Mexico. Some authors reported that the prevalence of this condition in this population ranged from 6% to 21.1% (5,30,32).

In 2020, González conducted a study to determine the prevalence of lipid profile alterations in students from two Mexican universities. Among their findings, HDL showed an alteration rate of 6.7% in the subjects. It was also emphasized that this condition could lead to the development of related diseases, which might play a decisive role in future cardiovascular and cerebrovascular conditions (33).

2.1.6. Arterial hypertension.

According to the ATP III guidelines, arterial hypertension is a multifactorial disease characterized by consistently high blood pressure, with a cutoff point of >130/85 mmHg (31). These values are associated with an increased risk of cardiovascular diseases, stroke, and chronic kidney diseases (12)

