6.3. Selection criteria

Table 4. Selection criteria

Inclusion	Exclusion	Elimination
University of Colima students linked to the central campus.	Motor limitations that may hinder the performance of physical exercise.	Musculoskeletal injuries during the study period.
Students aged between 18		Unforeseen Medical Events: Unexpected medical

and 25 years old.	Pregnancy or lactation.	situations that could influence study results, such as hospitalizations, serious illnesses, or surgeries.
Authorization to participate in the project with a signed informed consent.	High Vigorous Physical Activity Level according to the IPA-Q.	Non-Compliance with Follow-Up: Subjects failing to meet a minimum of 80% (19 out of 24 sessions) of the stipulated physical conditioning program time.
Suffer from at least one of the parameters of metabolic disorders or cardiovascular risk (Hyperglycemia, decreased DHL, elevated triglycerides, abdominal obesity or hypertension) following the clinical assessment (Considering the criteria established by the ADA and ATPIII).	To be currently under pharmacological treatment to manage altered metabolic levels.	Initiation of clinical treatment that may affect protocol results, such as medications that reduce alterations.
		Participants who voluntarily withdraw from the study.

Source: self-made.

7. Variable operationalisation.

Table 5. Dependent variables.

Dependent variables	Operational definition	Nature	Scale	Instrument
Glucose Alterations	Fasting plasmatic glucose concentration determination:	Quantitative Continuous Ratio	It is considered an alteration >110 mg/dl	Fasting serum glucose

Abdominal Circumference	Total abdominal perimeter Abdominal obesity based on abdominal circumference.	Quantitative Continuous Ratio	It is considered an alteration when: Males >90cm Females >85 cm	Circumferential measurement with ISAK tape measure
HDL (High-Density Lipoprotein)	Serum concentration of high-density lipoprotein in milligrams per deciliter (mg/dl)	Quantitative Continuous Ratio	It is considered an alteration when: Males < 40 mg/dl, Females < 50 mg/dl	Lipid profile test
Triglycerides	Serum concentration of triglycerides in milligrams per deciliter (mg/dl)	Quantitative Continuous Ratio	It is considered an alteration when: Males >150 mg/dl Females >150 mg/dl	Lipid profile test

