Arterial Hypertension	Subject's systolic and diastolic blood pressure measured in mercury millimeters (mmHg)	Quantitative Continuous Ratio	It is considered an alteration when: Males > 130/85 mmHg Females > 130/85 mmHg	Sphygmomanometer
Physical Activity Level	Physical Activity performed by the subject 7 days before the survey	Qualitative Ordinal	PA: Low, Medium, High	IPA-Q (International Physical Activity Questionnaire)
Physical Fitness Test: Aerobic	Subject's cardiorespiratory capacity using an	Qualitative Ordinal	Very Poor Poor Average	Quee's College Step Test

Capacity	effort test.		Good Excellent Superior	
----------	--------------	--	-------------------------------	--

Source: self-made based on the reference (11,105).

Table 6. Independent variables

Variable	Operational definition	Nature	Scale	Instrument
Aerobic physical exercise	Individually adapted aerobic physical exercise program meeting the WHO 2021 criteria and the FITT Principles.	Quantitative Continuous Ration	57% - 76%	Prescription

Source: self-made.

Table 7. Intervinient variables

Variable	Operational definition	Nature	Scale	Instrument
Age	Chronological age in years	Quantitative Continuous	18 - 24 years	Survey
Sex	Genetically corresponding sex	Qualitative Dichotomous nominal	Male and Female	Survey

Source: self-made.

8. Location for carrying out the protocol

University of Colima's Sports Center (central campus).

9. Study Procedure

Once the project is approved by the Bioethics Committee from the Faculty of Medicine at the University of Colima (Annex 1) and the Ethics Committee from Colima's Regional Hospital (Annex 2), annexing a no-conflict of interest letter (Annex 3), letters of intent will be prepared and sent to the directors of the faculties within the central campus of the University of Colima (Annex 4). Their purpose is to inform them about the project's generalities, obtain permission to share it with the students and address any questions they may have

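### Blood pressure decides entry and is an outcome, but the plan sets no number of readings or averaging rule, and the only procedure it describes yields one reading

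*Combined protocol and SAP*

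**What the plan says.** - **Role of blood pressure.** Table 4 (section 6.3) admits students who "Suffer from at least one of the parameters of metabolic disorders or cardiovascular risk", and hypertension is one of the five listed. Table 5 (section 7) makes systolic and diastolic pressure a continuous dependent variable. Section 5.3 names blood pressure in the hypothesis. Section 9 measures it at screening, after four weeks and after eight weeks, and the screening tests also serve as baseline.
- **Definition.** Section 2.1.6 describes hypertension as "characterized by consistently high blood pressure, with a cutoff point of >130/85 mmHg".
- **Procedure.** Section 2.2.3 has the subject sit for 5 to 10 minutes. Then "the handle of the manometer will be inflated until a pressure of 160 mmHg is reached", the valve is opened, and the operator proceeds by "listening in turn to the pulsations emitted by the body to determine systolic and diastolic blood pressure". If the values exceed the cut-offs given there, "an alteration in blood pressure must be confirmed". No repeat, interval or averaging rule follows.
- **Operational text.** For blood pressure, section 9 points to Annexe 8, which contains only a staging table.
- **Waist, for comparison.** Section 2.2.1, also background text, says: "Making at least two measurements and calculating their average (45) is recommended". Annexe 7, the operational waist procedure, mentions no repeat.

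**The concern.** An operator looking for instructions finds only section 2.2.3, and following it produces one systolic/diastolic pair. A single pair carries the full reading-to-reading error. That matters in three places:

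1. **Entry.** A student with no other qualifying parameter can be admitted on a chance high reading.
2. **Outcome.** The value at each of the three visits is noisier than the same visit could give.
3. **Baseline.** The value that admits the student is also the baseline, so students selected on a high reading will tend to read lower later without any exercise effect.

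Leaving the number of readings open brings a further risk: staff may repeat only when the first reading is high, so values would be obtained differently in different people.

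**Working it through.** **The plan's own figure.** The only calculation is in section 6.2: 6.2 × (22.53² + 12.88²) / (131.31 − 116.90)² = 6.2 × 673.49 / 207.65 = 20.1, taken as 20, and 20 × 1.2 = 24 per group. It reproduces. Section 2.4 reports the same means and SDs for triglycerides, so this figure says nothing about blood pressure precision and is unaffected by this point.

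**Assumptions.** The documents give no blood pressure variance, so all of these are assumed:
- within-visit reading-to-reading SD, w = 4-8 mmHg
- between-person SD, b = 8-12 mmHg
- visit-to-visit SD, v = 4-6 mmHg
- for entry, usual systolic pressure N(118, 10) and a cut-off of 130; diastolic pressure is ignored

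**Step 1. Variance of one visit's value.** With k readings it is b² + v² + w²/k.
- Smallest gain (b = 12, v = 6, w = 4): 196 with one reading, 188 with two, a 4% reduction.
- Largest gain (b = 8, v = 4, w = 8): 144 with one, 112 with two, a 22% reduction.

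**Step 2. Variance of a pre-post change.** The person's usual level cancels, leaving 2(v² + w²/k).
- Smallest gain (v = 6, w = 4): 104 against 88, a 15% reduction.
- Largest gain (v = 4, w = 8): 160 against 96, a 40% reduction.

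This supposes that everyone's true change is the same. Real differences in response would add to both variances and shrink the percentage. Section 11 does not say whether groups are compared on final values or on changes, so either step may apply.

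**Step 3. Chance flags at entry.** Let T be the usual value and R the recorded value. R has error variance e² = v² + w²/k and total SD s = √(100 + e²). The quantity wanted is P(T ≤ 130 given R > 130), from the bivariate normal distribution with correlation 10/s. Example (v = 4, w = 4, one reading): e² = 32, s = 11.49 and P(R > 130) = 0.148, and 41.6% of those flagged have T ≤ 130.

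| v | w | One reading | Mean of two |
|---|---|---|---|
| 4 | 4 | 42% | 37% |
| 4 | 8 | 57% | 49% |
| 6 | 4 | 50% | 47% |
| 6 | 8 | 61% | 55% |

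The gain is about 3 to 9 percentage points. Leaving out visit-to-visit variation (v = 0) would give 30-54% against 22-42%. That overstates the benefit, because a second reading on the same day cannot remove day-to-day variation.

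**Step 4. Sensitivity to prevalence.** N(118, 10) puts 11.5% of people truly above 130. The documents cite 25.5% (section 3) and 39.8% (Introduction). Suppose those were the shares with usual systolic pressure above 130. Keeping the SD at 10, the means become 123.4 and 127.4, and the formula in step 3 gives:
- at 25.5%: 29-44% with one reading, 26-39% with two
- at 39.8%: 21-32% with one reading, 18-28% with two

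**Step 5. Regression to the mean.** The expected excess of the recorded over the usual value among those flagged is (e²/s) × φ(c)/P(R > 130), where φ is the standard normal density and c = 12/s. Under N(118, 10) this is about 4 to 10 mmHg with one reading and about 3 to 8 with two. A fall of that size is expected later with no treatment effect in anyone flagged on blood pressure.

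**The case against.** **The documents nowhere say one reading.** This is correct. Section 2.2.3 is background text on how to take a measurement, and confirming an alteration could mean a repeat. A reader might infer that one reading per visit is a rule of the plan; the documents do not support that. What stands is that no other procedure exists, and the number of readings and the confirmation step are undefined.

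**The contrast with waist is weak.** A reader might infer that blood pressure was singled out for less care. The two-measurement advice for waist is a recommendation in background text, and Annexe 7 is as silent on repeats as Annexe 8.

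**Two readings on one day do not show consistently high pressure.** This is also correct. A same-day repeat reduces noise; it does not establish persistence.

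**Entry is not shown to be misclassified.** Any one of five parameters suffices, so only students eligible on blood pressure alone can enter by chance, and their share is unknown. The percentages in steps 3 and 4 describe people flagged on blood pressure, not the 48 participants.

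**The randomised comparison is not biased.** A reader might infer that chance entry distorts the treatment effect. Randomisation comes after screening, so chance flags and their later fall are expected equally in both groups. The cost there is precision. The protection does not extend to a within-group pre-post claim.

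**Conclusion.** The point holds as a minor, inexpensive improvement. The plan leaves the number of readings, the averaging rule and the meaning of confirmation unstated, and the only procedure it describes gives one reading. Under the assumed SDs, averaging two readings lowers visit-value variance by about 4-22% and change-score variance by 15-40%. It lowers the share of chance flags from 42-61% to 37-55% with usual systolic pressure N(118, 10); both figures are lower at the prevalences the documents cite. These sizes rest entirely on assumed variances; the direction does not. The precision loss concerns blood pressure in all participants, and the entry risk only those who qualify on blood pressure alone. The between-group estimate is not biased, but a within-group fall in blood pressure should not be read as an exercise effect. Section 11 does not list blood pressure among the variables for the paired tests, so whether such a claim is intended is unclear.

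**What to change.** In section 9 and Annexe 8:

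1. Specify at least two readings per visit after the seated rest already described, with a fixed interval, the same arm and the same device.
2. Use their mean for entry and for the outcome at baseline, week 4 and week 8.
3. Say what confirming an alteration involves, and state that same-day repeats reduce noise but do not show persistence.
4. Reconcile the device: stethoscope and arm cuff in section 2.2.3, a wrist digital monitor in Table 8.
5. Reconcile the cut-offs, which differ between section 2.2.3 (>130 and >80), section 2.1.6 and Table 5 (>130/85), Table 1 (the diastolic sign differs between women and men) and the staging table in Annexe 8.

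**Cost.** Two to three minutes per participant per visit with the same staff. For 48 participants and three visits that is 48 × 3 × 2 to 3 = 288 to 432 minutes in total, plus the same few minutes for each volunteer screened but not enrolled. A few borderline volunteers may no longer qualify on blood pressure alone. The planned sample size does not change.

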2.2.4. Testing and Diagnosis of Blood Glucose Alterations

To determine blood glucose alterations, a step-by-step process should be followed, starting with general recommendations. One of the most important steps is to fast for a minimum of 8 hours(49). The blood sample will be obtained through a venous puncture technique, filling a clinical tube specifically for fasting glucose testing. After collection, the tube will be taken to the laboratory for analysis(50). If the patient's results show >100 mg/dL to 125 mg/dL, they may be diagnosed with prediabetes(39).

2.3. Factors Associated with Metabolic Disorders in Higher Education Students

In 2022, the Pan American Health Organization (PAHO) reported that cardiovascular diseases accounted for the majority of deaths due to non-communicable diseases (NCDs), totalling 17.9 million deaths annually, while diabetes contributed to 1.6 million deaths worldwide(3). The risks that can exacerbate these figures include metabolic alterations such as Abdominal obesity, hypertension, HDL, triglycerides, glucose alterations, sedentary lifestyle and physical inactivity (51). These factors significantly impact young people and adolescents, since, worldwide, over 80% of them exhibit insufficient levels of physical activity (52). The WHO recommends adopting healthy practices, including quitting smoking, maintaining a balanced diet, achieving a healthy weight, reducing alcohol consumption, and minimizing sedentary behaviour and physical inactivity to mitigate the risks associated with these metabolic disorders(7,52,53).

2.3.1. Unbalanced diet as a risk factor in metabolic disorders among higher education students

Diet, in addition to serving as a fundamental human need, fulfils various societal functions related to cultural customs, socioeconomic factors, and even shared events that reflect collective well-being (54).

PAHO determined that eating habits are established during childhood and adolescence, influenced by various channels of interaction, including family dynamics. However, over time, social circles, lifestyle, and dietary patterns evolve to align with sociocultural trends and demands (55). When students enter university life, they often move away from their family nucleus, leading to an adjustment to new living situations. Economic circumstances, cooking skills, and dietary customs shared with peers all play a role in this adaptation (54).

Therefore, the lifestyle changes associated with the start of university life significantly impact both physical and mental health. Many young individuals exhibit inadequate eating habits, characterized by excessive consumption of fast food, skipping breakfast, irregular meal times, and high intake of meat, sweets, pastries, and sodas as their main beverages. These dietary patterns negatively affect overall nutritional status and health (54, 56).

According to perspectives from Ramos 2020, Lozano 2021, and ENSANUT 2022, nutrition surveys reveal that Mexican higher education students have obesity rates ranging from 48.6% to 72.5%, which is highly detrimental to cardiovascular health, especially when combined with the widespread physical inactivity and sedentary behaviour observed among young individuals (5, 25).

2.3.1. Sedentary lifestyle and physical inactivity as a risk factor in metabolic disorders in higher education students.

The World Health Organization (WHO) and Silveira in 2022 define physical inactivity as failing to engage in 150 minutes of moderate-intensity physical activity or 75 minutes of

vigorous-intensity activity per week. Likewise, they define sedentary behaviour as engaging in activities with a basal energy expenditure equal to or less than 1.5 METs (unit of measurement for metabolic rate or energy consumed while at rest) (annexe 12). Examples of such activities include sitting for long hours at university or home, lying down, looking at a cell phone, or doing desk work (52,57).

According to the PAHO and the National Health and Nutrition Survey (ENSANUT) in 2022, physical inactivity levels in Latin America increased from 33% to 39% (58). In Mexico, there has been a growth from 14% in 2016 to 20.8% in 2018(59). The latest ENSANUT report reveals that 42.6% of adolescents aged 15 to 19 don't accumulate an average of at least 60 minutes per day of moderate or vigorous physical activity (MVPA), 90.8% of them spend >2 hours daily in front of screens, and 48.1% of adolescents aged 14 to 17 do not get the recommended sleep duration for their age (8 to 10 hours per day) (60).

In a study conducted by the National Autonomous University of Mexico (UNAM), researchers identified the precursor factors for metabolic alterations that students at the university might experience. Upon collecting this information, the results revealed that 56% of the university population is sedentary, and 90% reported inadequate dietary habits. With such compelling parameters, the author asserts that this population is at high risk of developing metabolic disorders in the short or long term, thereby compromising their cardiovascular health(7). Additionally, a study assessed the cardiorespiratory fitness VO₂max of medical students using the Queens College Step Test (a method to determine cardiorespiratory fitness based on maximum oxygen consumption). The results indicated that the subjects had moderate cardiorespiratory fitness, associated with physical inactivity, sedentary behaviour, and unhealthy dietary changes, further increasing the risks of metabolic alterations(61).

Therefore, in 2022, the World Health Organization (WHO) and the Pan American Health Organization (PAHO) recommended engaging in physical activity for at least 150 minutes per week. This can be broken down into 75 minutes of vigorous activity and another 75 minutes following the aerobic metabolic pathway to maximize oxygen transport across different body systems(1,58). Likewise, there is evidence that aerobic exercise, adhering to the principles of

Frequency, Intensity, Time, and Progress (FIIT), can positively influence the reduction of these metabolic alterations, potentially restoring balance(62).

Silveira in 2022, and Basto and Medina in 2023 have highlighted that inactive individuals who gradually transition to moderate physical activity (MPA) do not face known risks of sudden cardiac events, decrease metabolic alterations and have minimal chances of bone, muscle, or joint injuries(40,57,60). Individuals accustomed to MPA can gradually progress to vigorous physical activity (VPA)(63).

